### **3.4.4.4. PARENT/CAREGIVER OUTCOME MEASURES**

Parent(s)/Caregiver(s) assessment of the clinical condition of the subject will be done by daily completion of a diary during the hospital stay and up to the EOS (Day 28) visit. The diary will be used to measure three respiratory symptoms (cough, [audible] wheeze, and trouble breathing), to score the general health of the subject and will ask for use of health care utilization and medication for respiratory symptoms.

The three respiratory symptoms (cough, trouble breathing and wheezing) will be scored from not present over very mild, mild, moderate, and severe up to very severe.

The global rating of the child's health by the parent(s)/caregiver(s) will be captured by a VAS. The parent or caregiver will make a mark between 0 ("very bad") and 100 mm ("perfect") on the scale to indicate the subject's current health. In addition, the parent(s)/caregiver(s) will indicate when the child was back to his/her condition as before the RSV infection started.

## **3.4.5. PHARMACOKINETIC ASSESSMENTS**

### **3.4.5.1. SAMPLE COLLECTION AND HANDLING**

Throughout the study, blood samples will be taken for analysis of ALX-0171 concentrations in serum, according to the time points defined in the [Schedule of Assessments](#).

- Subjects not undergoing the more extensive blood sampling scheme will have 1 blood sample taken on Day 2 or 3, at any time between 0.5 hours after completion of the second dose and initiation of the administration of the third dose.
- Subjects undergoing the more extensive blood sampling scheme will have 3 blood samples taken on Days 2-3: 1) pre second dose, 2) at any time between 0.5 hours and 3 hours after completion of the second dose, and 3) at any time between 3 hours and 6 hours after completion of the second dose (and at least 1 hour apart from the previous sampling).

The exact dates and times of blood sampling will be recorded.

The blood samples for PK assessments will be collected from a vein, as using capillary blood (e.g., from heel pricks) is not allowed. Anesthetic cream or spray can be used to minimize the subject's discomfort and distress. For further details on sample collection, shipment, storage and processing, please refer to a separate Lab Manual.

### **3.4.5.2. BIOANALYSIS**

Determination of ALX-0171 concentrations in serum will be done by a validated Ligand Binding Assay (LBA)-based method at a designated analytical laboratory according to the bioanalytical methodology and procedures described in a separate Bioanalytical Analysis Plan. All PK samples (both from placebo and ALX-0171 treated subjects) will be analyzed for measurement of ALX-0171.

## **3.4.6. PHARMACODYNAMIC ASSESSMENTS**

### **3.4.6.1. SAMPLE COLLECTION AND HANDLING**

Exploratory analysis of KL-6 levels will be done according to the time points defined in the [Schedule of Assessments](#).

KL-6 will be assessed on the remainder (if any) of the blood samples obtained for PK or immunogenicity testing, once the appropriate volume for their intended purpose has been extracted.

### **3.4.6.2. BIOANALYSIS**

Determination of KL-6 levels in serum will be done by validated methods at the Sponsor. Bioanalytical procedures will be described in a separate Bioanalytical Analysis plan.

### **3.4.7. IMMUNOGENICITY**

#### **3.4.7.1. SAMPLE COLLECTION AND HANDLING**

To assess systemic immunogenicity of ALX-0171, blood samples will be collected at the time points defined in the [Schedule of Assessments](#). If ADA are present, a further evaluation of their neutralizing capacity will be performed.

Note: In case no sample was taken at the screening visit, a blood sample for assessment of immunogenicity should be collected at the Day 1 pre-dose timepoint, as far as possible. In case no sample was taken at the FU (Day 14) visit, a blood sample for assessment of immunogenicity should be collected at the EOS (Day 28) visit, as far as possible.

The exact date and time of blood sampling will be recorded.

The blood samples for ADA assessments will be collected from a vein, as using capillary blood (e.g., from heel pricks) is not allowed. Anesthetic cream or spray can be used to minimize the subject's discomfort and distress. For further details on sample collection, shipment, storage and processing, please refer to a separate Lab Manual.

Of note, an additional serum sample should be collected (if reasonably feasible) in case of serious and/or severe hypersensitivity reaction (blood volume: 1 mL and collected as soon as possible after the start of the event) to allow characterization of the reaction if deemed required (also see section [3.4.8.1](#)).

#### **3.4.7.2. BIOANALYSIS**

Determination of ADA will be done using a validated screening, confirmation and titration ADA bridging assay, with further characterization of ADA positive samples by a competitive ligand binding neutralizing antibody assay. The immunogenicity data will be processed according to a dedicated Bioanalytical Analysis plan.

Bioanalytical procedures for the additional sample in case of serious and/or severe hypersensitivity reaction will be described in a separate Bioanalytical Analysis plan.

### 3.4.8. ASSESSMENTS OF SAFETY

Safety assessments consist of AE reports (including SAEs, hypersensitivity reactions), clinical laboratory assessments, heart rate and SpO2, respiratory rate, body weight, body temperature, physical examination, and lung auscultation.

The time points are defined in the [Schedule of Assessments](#).

At each of the time points indicated in the [Schedule of Assessments](#), a physical examination should be performed, including heart auscultation, examination of abdomen, skin and ears/nose/throat. Lung auscultation is to be performed more frequently and is therefore listed separately in the Schedule of Assessment.

The parent(s)/legal guardian(s) will receive a subject card, indicating the address and phone number of the Investigator and/or other relevant emergency contact details (including e.g., subject number, medication number). The subject's parent(s)/legal guardian(s) will be advised to carry this card with them throughout the study so that the appropriate actions can be undertaken in case of emergency. They will also be advised to contact the Investigator (or his/her designee) with any medical and/or safety concern.

In order to appropriately document possible events after discharge from the hospital, a diary will be completed by the parent(s) or caregiver(s) and be brought to the site at the FU visit on Day 14 and EOS visit on Day 28.

#### 3.4.8.1. ADVERSE EVENTS

General information on evaluation and reporting of AEs is provided in section [3.5](#).

It is the responsibility of the Investigator to collect all AEs (both serious and non-serious) resulting from spontaneous, unsolicited reports by parents/caregivers and/or by healthcare staff, by observation (by the Investigator and/or healthcare staff), by routine open questioning of the parents/caregivers by the Investigator (e.g., "Is there anything new that you wish to discuss?") and by reviewing the diary with the parent(s)/caregiver(s).

All AEs occurring between the time a signed and dated ICF is obtained until completion of the subject's last visit must be documented in the source documents and the eCRF.

Criteria for determining whether an abnormal objective test finding (e.g., laboratory result), a complication of a protocol mandated procedure (e.g., blood draw), or a change in physical examination findings should be reported as an AE include, but are not limited to:

1. Result/finding is associated with accompanying clinical signs and symptoms (new onset or aggravated in severity or frequency from baseline condition), and/or
2. Result/finding requires extra diagnostic testing (other than diagnostic exclusion tests) or medical/surgical intervention, and/or

3. Result/finding would require a premature discontinuation from the study drug, significant additional concomitant drug treatment or other therapy, and/or
4. Result/finding leads to any of the outcomes included in the definition of an SAE, and/or
5. Result/finding is considered to be an AE by the Investigator.

Any abnormal test result that is determined to be an error and merely repeating an abnormal test does not require reporting as an AE.

Airway hyperresponsiveness and immediate or delayed adverse drug reactions should be managed according to the Investigator's clinical judgment and applicable standard of care.

- If airway hyperresponsiveness would occur, administration of a bronchodilator like the short-acting  $\beta$ 2-agonist salbutamol may be administered (with an appropriate follow-up period) according to the investigator's assessment of the particular reaction and subject's characteristics.
- With regard to immediate or delayed hypersensitivity reactions, measures beyond basic supportive care are not considered necessary for subjects with purely local reactions. Subjects with suspected systemic hypersensitivity, however, should be admitted or treated and observed for a longer period, preferably in the emergency department or another close-observation area, depending on the severity of the reaction and its hemodynamic impact.

In case of severe and/or serious hypersensitivity reactions, an additional serum sample should be collected (if reasonably feasible) as soon as possible after the start of the event (blood volume: 1 mL) to characterize the reaction (if deemed required). As described in section 3.2.3, subjects must be discontinued from study drug treatment in case of a severe and/or serious hypersensitivity reaction, a severe and/or serious acute respiratory distress reaction induced by study drug, or when a subject needs to start non-invasive respiratory support or ventilation.

Occurrence of episodes of apnea will be captured together with the overall hospitalization information and should be reported as an AE. As defined by the American Academy of Pediatrics, apnea is "an unexplained episode of cessation of breathing for 20 seconds or longer, or a shorter respiratory pause associated with bradycardia, cyanosis, pallor, and/or marked hypotonia."

In addition to the events meeting the seriousness criteria mentioned in section 3.5.2, the following events will trigger a SAE reporting:

- Transfer to ICU.
- Initiation of non-invasive respiratory support (including start of HFOT or increasing the flow above the allowed level) or invasive ventilation.
- Episodes of apnea that fulfil the seriousness criteria.

### **3.4.8.2. LABORATORY ASSESSMENTS**

Blood samples for clinical laboratory analyses will be collected at the time points indicated in the [Schedule of Assessments](#).

Safety lab assessments will be performed by the local laboratory in order to allow for timely availability of the results. For local laboratory data, the local normal ranges and laboratory accreditation are to be collected/provided.

If all hematology and biochemistry blood parameters required for the study are already known from analysis done as a routine assessment upon arrival at the hospital, collection of screening clinical laboratory samples does not need to be repeated for the purpose of this study. However, the samples should be analyzed at the same local laboratory that will be used for the remainder of the study.

The blood samples will be collected according to the site's standard practice. Anesthetic cream or spray can be used to minimize the subject's discomfort and distress.

The following tests will be included in the clinical laboratory analysis:

- Clinical chemistry: alanine aminotransferase, aspartate aminotransferase, creatinine, sodium, potassium, chloride, C-reactive protein,  $\gamma$ -glutamyl-transferase, blood urea nitrogen
- Hematology: hemoglobin, hematocrit, red blood cell count and indices, mean corpuscular hemoglobin, mean corpuscular hemoglobin concentration, platelet count (or estimate), white blood cell count including differential (lymphocytes, neutrophils, monocytes, basophils, eosinophils).

Clinical relevance of values outside the local laboratory's normal range will be assessed by the Investigator. All clinically significant laboratory findings will be recorded as AEs in the eCRF (also see section [3.4.8.1](#)).

In the event of unexplained or unexpected clinical laboratory test values, the test(s) may be repeated and followed up until the results have returned to the normal range and/or an adequate explanation for the abnormality is found.

### **3.4.8.3. LUNG AUSCULTATION**

At each of the time points indicated in the [Schedule of Assessments](#), a lung auscultation will be performed to assess wheezing, crackles/crepitation and other abnormalities in lung auscultation.

A new finding or a change of a finding that is judged as an undesirable medical event shall be reported as an AE.

In case the subject is re-hospitalized or consults the Investigator for a respiratory condition after hospital discharge up to the EOS (Day 28) visit, an unscheduled visit is to be performed that will include a lung auscultation assessment (in addition to a physical examination and collection of a nasal swab) (see section 3.4.1.3).

#### **3.4.8.4. PHYSICAL EXAMINATION**

At each of the time points indicated in the [Schedule of Assessments](#), a physical examination should be performed, including heart auscultation, examination of abdomen, skin and ears/nose/throat.

Physical examination will be recorded as "normal", "abnormal, not clinically significant" or "abnormal, clinically significant" at every assessment. A new finding or a change of a finding that is judged as an undesirable medical event (including all findings recorded as "abnormal, clinically significant") shall be reported as an AE.

In case the subject is re-hospitalized or consults the Investigator for a respiratory condition after hospital discharge up to the EOS (Day 28) visit, an unscheduled visit is to be performed that will include a physical examination (in addition to a lung auscultation and collection of a nasal swab) (see section 3.4.1.3).

#### **3.4.8.5. HEART RATE AND $S_pO_2$**

The collection of these parameters is described in section 3.4.4.3 as the evolution of the heart rate and oxygen saturation levels will also inform on clinical activity outcome.

#### **3.4.8.6. BODY WEIGHT, HEIGHT, AND TEMPERATURE**

At the time points indicated in the [Schedule of Assessments](#), the following parameters will be assessed: body height, weight, and temperature.

To obtain the actual body weight, subjects must be weighed lightly clothed.

Temperature is to be measured preferably rectal, oral, or tympanic (axillary method less preferred). For each individual subject, the same method should be used throughout the study as far as possible. The method will be recorded in the eCRF.

### 3.4.9. TOTAL BLOOD VOLUME

The blood samples will be used i) for safety evaluation (clinical laboratory: hematology and clinical biochemistry), ii) to monitor the systemic concentration of ALX-0171 (as a surrogate measure of the local lung concentration), and iii) to assess potential immunogenicity (Table 2).

If all hematology and biochemistry blood parameters required for the study are already known from analysis done as a routine assessment upon arrival at the hospital, collection of screening clinical laboratory samples does not need to be repeated for the purpose of this study. However, the samples should be analyzed at the same local laboratory that will be used for the remainder of the study.

Exploratory biomarker will only be assessed on the remainder of the blood samples once the appropriate volume for their intended purpose has been extracted. An additional serum sample should be collected (if reasonably feasible) in case of serious and/or severe hypersensitivity reaction (volume of 1 mL). Note that no human DNA or RNA analysis will be performed.

The precise assessments that are intended to be performed on each of the blood samples are arranged by priority; when insufficient volume is available (e.g., because of difficulties in or limits to obtaining blood), only the highest priority(ies) will be assessed (see Table 2).

Of note: for subjects with a body weight below 5 kg (irrespective of whether they undergo the more extensive blood sampling scheme or not), the sample for analysis of immunogenicity at screening and on Day 14 should not be collected in case blood volume needed for local assessment of clinical laboratory parameters exceeds 2.5 mL (in order to not exceed the maximum blood volume allowed to be collected at a single time point). Instead and if possible, the blood sample for immunogenicity should be collected at Day 1 pre-dose (replacing the screening sample) and at the EOS (Day 28) visit (replacing the FU visit sample).

In the 48 subjects undergoing more extensive sampling, 5 blood samples will be taken (for evaluation of clinical safety, PK, and immunogenicity) with a total estimated volume of 3.5 mL (not including volumes for local lab assessments). In the remainder of subjects, 3 blood samples will be taken with a total estimated volume of 2.5 mL (not including volumes for local lab assessments).

If permitted by local regulations, blood samples that remain after protocol-specific assessments have been performed may be used by the Sponsor for further exploratory work in the context of the development of ALX-0171 or evaluation of RSV. These samples may be

**Ablynx NV****Clinical Study Protocol ALX0171-C201****Final v3.0**

kept for up to 5 years after the end of the study. No human DNA or RNA analysis will be performed.

**Table 2: Timing, priority and estimated volume of scheduled blood draws**

Sample	Priority	Maximal Target volume
1 blood draw at Screening a	1. Clinical laboratory: - Hematology (whole blood) - Biochemistry (serum) 2. Immunogenicity (serum) b 3. Exploratory biomarker c	- whole blood for hematology (volume according to local practice) - whole blood to be processed into serum for biochemistry (volume according to local practice) - 1 mL whole blood, to be processed into serum for immunogenicity and biomarker b Total: 1 mL whole blood + volume needed for clinical laboratory
1 blood draw on Day 2 or 3 OR 3 blood draws on Days 2-3 (in 48 subjects) 1 blood draw during the Day 14 FU visit	1. PK (serum) 2. Exploratory biomarker c	- 0.5 mL whole blood, to be processed into serum for PK and biomarker b Total: 0.5 mL whole blood in case of 1 blood draw or 1.5 mL whole blood in case of 3 blood draws
	1. Clinical laboratory: - Hematology (whole blood) - Biochemistry (serum) 2. Immunogenicity (serum) b 3. Exploratory biomarker c	- whole blood for hematology (volume according to local practice) - whole blood to be processed into serum for biochemistry (volume according to local practice) - 1 mL whole blood, to be processed into serum for immunogenicity and biomarker b Total: 1 mL whole blood + volume needed for clinical laboratory

a. If all hematology and biochemistry blood parameters required for the study are already known from analysis done as a routine assessment upon arrival at the hospital, collection of screening clinical laboratory samples does not need to be repeated for the purpose of this study. However, the samples should be analyzed at the same local laboratory that will be used for the remainder of the study.

b. For subjects with a body weight below 5 kg (irrespective of whether they undergo the more extensive blood sampling scheme or not) and in case blood volume needed for local clinical laboratory exceeds 2.5 mL, the sample for analysis of immunogenicity should not be collected at screening and on Day 14 but at Day 1 pre-dose and Day 28, as far as possible.

c. Only if sufficient blood volume (serum) is available after analyzing the samples obtained for PK or immunogenicity.

### **3.4.10. APPROPRIATENESS AND TIMING OF MEASUREMENTS**

The assessments which will be made in this study are standard and generally recognized as reliable, accurate, and relevant.

The timing of all assessments is detailed in the [Schedule of Assessments](#).

Throughout the study, study personnel should make every reasonable effort to follow the timing of assessments and procedures in the Schedule of Assessments for each subject.

## **3.5. ADVERSE EVENT EVALUATION AND REPORTING**

### **3.5.1. ADVERSE EVENTS**

Study-specific information on evaluation and reporting of AEs is provided in section [3.4.8.1](#).

AE definitions will be consistent with the “Note for Guidance on clinical safety data management: definitions and standards for expedited reporting” (International Conference on Harmonization [ICH] topic E2A).

An AE is any untoward medical occurrence in a clinical study subject administered a medicinal (investigational or non-investigational) product. An AE does not necessarily have a causal relationship with the treatment. An AE can therefore be any unfavorable and unintended sign (including an abnormal finding), symptom, or disease temporally associated with the use of a medicinal (investigational or non-investigational) product, whether or not considered related to that medicinal (investigational or non-investigational) product.

This includes any occurrence that is new in onset or aggravated in severity or frequency from the baseline condition, or abnormal results of diagnostic procedures, including laboratory test abnormalities.

In differentiating between medical history and AEs, the following points will be considered:

- Conditions that started before signing of informed consent and for which no symptoms or treatment are present up to the timing of signing of informed consent are recorded as medical history (e.g., seasonal allergy without acute complaints).
- Conditions that started before signing of informed consent and for which symptoms or treatment are present after signing of informed consent, but with unchanged severity, are recorded as medical history (e.g., allergic pollinosis).
- Conditions that started or deteriorated after signing of informed consent will be documented as AEs.

All AEs will be reported from the time a signed and dated ICF is obtained until completion of the subject’s last visit.

A TEAE is any AE temporally associated with the use of study drug, whether considered related to the study drug or not. TEAEs are recorded from the start of study drug administration, until completion of the subject’s last visit.

All AEs will be assessed by the Investigator and recorded in the patient medical records and on the AE eCRF page. AE entry should indicate time of onset and end time and rating of the seriousness (see section 3.5.2), severity (see section 3.5.1.1), and outcome (see section 3.5.1.2) of the AEs, relationship to study drug and study procedures (see section 3.5.1.3), action taken regarding study drug (see section 3.5.1.4), and concomitant therapy taken for the AE.

The Investigator will judge upon the severity of the AEs and relation to study drug and study procedures.

### **3.5.1.1. AE SEVERITY**

The severity of AEs will be rated on a 3-point scale:

- Mild: discomfort noticed but no disruption of normal daily activity
- Moderate: discomfort sufficient to reduce or affect normal daily activity
- Severe: incapacitating with performing normal daily activity

It is emphasized that the term severe is a measure of intensity: a severe AE is not necessarily serious. For example, itching for several days may be rated as severe, but may not be clinically serious.

### **3.5.1.2. OUTCOME**

The outcome of the AE is to be documented as follows:

- Recovered/resolved
- Recovering/resolving
- Recovered/resolved with sequelae
- Not recovered/not resolved
- Fatal
- Unknown

### **3.5.1.3. RELATION TO STUDY DRUG OR STUDY PROCEDURES**

The assessment of the causal relationship between an AE and the administration of treatment is a clinical decision based on all available information at the time of the completion of the eCRF.

The assessment is based on the question whether there was a “reasonable causal relationship” to the study treatment in question. Possible answers are:

- Not related
- Unlikely related
- Possibly related
- Related
- Not applicable

Note that only AEs starting after administration of study drug can be assigned a causal relationship between the AE and study drug administration. For AEs starting prior to study drug administration, causal relationship between the AE and study drug should be “not applicable”.

Assessment of causal relationship of any AE to protocol-required procedures can be completed with:

- Yes (specify)
- No

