## 8 SAFETY

### 8.1 Adverse Events

#### 8.1.1 Definitions

An AE is defined as any untoward medical occurrence in a clinical study subject administered a medicinal (investigational or non-investigational) product. An AE does not necessarily have a causal relationship with the treatment. All AEs will be reported from the time a signed and dated ICF is obtained until completion of the subject's last visit.

A treatment emergent adverse event (TEAE) is defined as any adverse event starting or worsening in severity (for pre-existing conditions) from the start of study drug administration, until completion of the subject's last visit.

All tables will only present TEAE. Pre-treatment AEs will only be listed.

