#### 8.1.4 Drug relatedness

Following ICH-E3, the drug relatedness as assessed by investigator will be dichotomized as follows:

- Drug related: at least possibly drug related, or with a missing drug relatedness
- Not drug related: less than possibly drug related.

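### Causality is rated by AE onset only, but treatment emergence also by worsening, so a pre-dose AE that worsens after dosing can be a TEAE with no relatedness rating and no defined place in the related-event tables

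*Protocol*

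**What the plan says.** Protocol 3.5.1.3 lists five possible answers to the causality question, one of which is 'not applicable'. It then restricts their use: "Note that only AEs starting after administration of study drug can be assigned a causal relationship between the AE and study drug administration". The next sentence fixes the answer for the rest: "For AEs starting prior to study drug administration, causal relationship between the AE and study drug should be" 'not applicable'. Neither sentence makes an exception for an AE that gets worse after dosing.

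SAP 8.1.1 uses a wider test for treatment emergence: "any adverse event starting or worsening in severity (for pre-existing conditions) from the start of study drug administration", up to the last visit. It adds: "All tables will only present TEAE. Pre-treatment AEs will only be listed".

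SAP 8.1.4 reduces relatedness to two categories. The first is "Drug related: at least possibly drug related, or with a missing drug relatedness". The second is "Not drug related: less than possibly drug related". The answer 'not applicable' is not mentioned.

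Protocol 3.5.1 counts aggravation within the definition of an AE: "This includes any occurrence that is new in onset or aggravated in severity or frequency from the baseline condition". It also has conditions that deteriorate after consent documented as AEs. Neither document says whether an AE that began before dosing and worsened afterwards keeps its record and onset or is entered again as a new AE.

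**The concern.** The two documents classify the same event on different clocks. The protocol asks when the AE began. The SAP asks when it began or worsened. An event can satisfy the SAP's test for treatment emergence while the protocol tells the Investigator not to rate its relationship to study drug.

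The relatedness field has several uses. SAP 8.1.7 tabulates subjects with treatment-related TEAEs and with serious treatment-related TEAEs, and Table 14.3.1.6 breaks related events down by relationship. Protocol 3.5.3 makes SUSAR status depend on a relationship that is at least possible. Safety by dose is part of the primary objective, and the first potential risk described in Protocol 1.3.3 is airway hyperresponsiveness, in infants who already have respiratory illness. Aggravation of an existing respiratory event is therefore a plausible form of harm, and its attribution should not depend on how a site fills in the AE page.

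**Working it through.** The documents state no figure to reproduce, and the point rests on definitions. The check follows an event through the rules.

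**The exposed window.** AEs are collected from consent (Protocol 3.4.1). Randomization is within 24 hours of hospital arrival (Protocol 3.4.1.1) and the first dose within 3 hours of randomization (Protocol 3.3.7). If consent is given at or after arrival, the time from consent to first dose is at most 24 + 3 = 27 hours.

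**Three cases.**

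| Case | Onset on the record | Causality under Protocol 3.5.1.3 | TEAE under SAP 8.1.1 | Category under SAP 8.1.4 |
|---|---|---|---|---|
| A. Condition present before consent and stable until dosing, then deteriorates; the deterioration is the AE | After dosing | Can be rated | Yes | Defined |
| B. AE starts between consent and dosing, worsens after dosing; worsening entered as a new AE | After dosing | Can be rated | Yes | Defined |
| C. Same as B, but kept as one record | Before dosing | 'Not applicable' | Yes, if the worsening clause covers it | Undefined |

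Only case C is a problem. A condition that predates consent can also reach it: if it first deteriorates between consent and dosing, it becomes an AE at that point, and a second deterioration after dosing puts it in case B or C.

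**Does the plan steer sites towards B or C?** Two texts suggest that C can occur. First, the worsening clause in SAP 8.1.1 adds something only if some worsened events keep a pre-dose start; if every worsening had its own post-dose onset, the word for starting would already cover it. Second, Protocol 3.5.1 asks each AE entry for onset, end and ratings but names no date of a change in severity. SAP 14.3.1.1, on incomplete dates, likewise decides treatment emergence from the start date, with the end date as a check, and has no rule for worsening. On the other side, Protocol 3.5.1 treats aggravation as an AE, and Protocol 3.4.8.3 has a changed auscultation finding reported as an AE when it is judged undesirable. Both point to B. The plan permits either practice.

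**Where does 'not applicable' go?** It is a recorded answer, so it is not plainly missing, which would make it drug related. Nor is it plainly below 'possibly'. The programmer has to choose, with no rule fixed in advance.

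**A further ambiguity.** The SAP's worsening clause speaks of pre-existing conditions. If that phrase were read to exclude AEs that began after consent, a case C event would count as pre-treatment and be listed only, outside every TEAE table.

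**The case against.** The strongest reply is that the protocol already makes a worsening reportable in its own right. A post-dose aggravation entered that way has a post-dose onset and can be rated. This stands, and it confines the problem to case C. The eCRF completion guidelines mentioned in Protocol 5.2.1 are not among the documents and may already require a separate entry.

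A second reply also largely stands: the RSV illness itself predates consent (inclusion criterion 6 requires symptoms by screening), so most post-inhalation deterioration of that illness falls in case A.

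Third, a worsened event that counts as a TEAE still appears in the overall, serious, severe and drug-withdrawn counts of SAP 8.1.7, and SAEs are listed whatever their treatment emergence. Only the attributed subset is affected, and it is compared between randomized, blinded groups.

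Two stronger readings are tempting, and the documents do not support them. A reader might infer that drug-induced worsening can never be counted as drug related. That ignores cases A and B, and SAP 8.1.4 leaves 'not applicable' unplaced; it does not exclude it. A reader might also infer that such an event could not trigger the stopping criteria. Those criteria (Protocol 3.1.1) turn on what the Investigator considers related and do not name the eCRF field. Protocol 3.5.2 requires a relationship assessment on every SAE Form. The IDMC receives SAE information in real time and reviews cumulative unblinded safety data whatever the attribution.

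What remains is that no rule says which record a worsened pre-dose AE belongs on, that the one explicit causality rule looks at onset alone, and that one of its permitted answers has no category in the SAP.

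**Conclusion.** The inconsistency is real and narrow. It affects AEs that start in the window of at most about 27 hours between consent and first dose, worsen after dosing, and are kept as one record with the pre-dose onset. For these, relatedness is not assessed and the category in the treatment-related tables is undefined. The documents give no count of such events, and it is probably small. The share that one infant makes up of a dose group or safety cohort would not measure the problem, since any single subject carries that weight in any count.

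The conclusion assumes that the SAP's worsening clause covers AEs that began after consent, and that the eCRF guidelines do not already require a new record. If they do, only the mapping of 'not applicable' is left to settle. The change is still worth making, because it protects the related-event tables and the SUSAR test and is almost free.

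**What to change.** 1. **Protocol 3.5.1.3 and the eCRF completion guideline.** Limit 'not applicable' to AEs that neither start nor worsen after the first dose. State that a post-dose worsening is entered as a new AE with its own onset, severity and causality.
2. **SAP 8.1.4.** Add one line: any remaining TEAE with causality 'not applicable' is handled like missing relatedness and counted as drug related. This matches the SAP's own conservative handling of missing relatedness and of incomplete onset dates (SAP 8.1.3).

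For records already completed under the onset-only rule, the SAP line takes effect without going back to sites.

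The cost is a sentence or two in the protocol and guideline and one line in the SAP. The number of events counted as related may rise slightly, and some of those will be events that an Investigator would have rated unrelated if asked.
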